7.1.8 Follow-up for efficacy evaluations

Patients who discontinue treatment for reasons other than irRECIST PD will have tumor assessments per [Table 7-1](#) until withdrawal of consent, death, lost to follow-up or eventual irRECIST PD per BIRC even if new post treatment ANP is started.

[figure not shown]
After the primary analysis cut-off date (10-Aug-2018), post-treatment efficacy follow-up will be discontinued. Therefore, for patients who discontinue study treatment for any reasons after the primary analysis cut-off date, post treatment efficacy follow-up will not be performed and these patients will enter the safety follow-up. If clinically indicated, patients may continue to undergo tumor response assessments during the safety follow-up according to local or institutional standard of care; however, these tumor response assessments will no longer be reported in the eCRF.

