disappear in which case a CR assignment is applicable. In studies where confirmation of response is not required after a single PR the overall lesion response should still be considered PR (or UNK) until progression is documented or the lesion totally disappears in which case a CR assignment is applicable.

Example: In a case where confirmation of response is required the sum of lesion diameters is 200 mm at baseline and then 140 mm - 150 mm - 140 mm - 160 mm - 160 mm at the subsequent visits. Assuming that non-target lesions did not progress, the overall lesion response would be PR - SD - PR - PR - PR. The second assessment with 140 mm confirms the PR for this patient. All subsequent assessments are considered PR even if tumor measurements decrease only by 20% compared to baseline (200 mm to 160 mm) at the following assessments.

If the patient progressed but continues study treatment, further assessments are not considered for the determination of best overall response.

Note: these cases may be described as a separate finding in the CSR but not included in the overall response or disease control rates.

The best overall response for a patient is always calculated, based on the sequence of overall lesion responses. However, the overall lesion response at a given assessment may be provided from different sources:

- Investigator overall lesion response
- Central Blinded Review overall lesion response
- Novartis calculated overall lesion response (based on measurements from either Investigator or Central Review)

The primary analysis of the best overall response will be based on the sequence of investigator/central blinded review/calculated (investigator)/calculated (central) overall lesion responses.

Based on the patients' best overall response during the study, the following rates are then calculated:

Overall response rate (ORR) is the proportion of patients with a best overall response of CR or PR. This is also referred to as 'Objective response rate' in some protocols or publications.

Disease control rate (DCR) is the proportion of patients with a best overall response of CR or PR or SD. The objective of this endpoint is to summarize patients with signs of "activity" defined as either shrinkage of tumor (regardless of duration) or slowing down of tumor growth.

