2.5.1 Primary endpoint

ORR is defined as the proportion of patients with best overall response (BOR) of complete response (CR) or partial response (PR) according to RECIST 1.1 (see Appendix 1 of the study protocol). ORR will be calculated within each group based on the FAS using BIRC review of tumor assessment data. Patients with only non-measurable disease at baseline will be part of the analysis and will be included in the numerator only if a complete response was observed. Tumor assessments performed before the start of any further antineoplastic therapy (i.e. any additional secondary antineoplastic therapy or surgery) will be considered in the assessment of BOR. Limited-field palliative radiotherapy administered as concomitant therapy per protocol will not

be considered as new antineoplastic therapy. Localized radiotherapy and treatment with bisphosphonates for pre-existing, painful bone/liver metastases is permitted.

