Waterfall graphs will be used to depict the anti-tumor activity. These plots will display the best percentage change from baseline in the sum of diameters of all target lesions for each patient. Only patients with measurable disease at baseline will be included in the waterfall graphs. Special consideration is needed for assessments where the target lesion response is CR, PR or SD, but the appearance of a new lesion or a worsening of non-target lesions results in an overall lesion response of PD. As a conservative approach, such assessments will not be considered for display as bars in the graph, since the percentage change in the sum of diameters of target lesions reflects the non-PD target lesion response, but the overall lesion response is PD. A patient with only such assessments will be represented by a special symbol (e.g. □) in the waterfall graph. Assessments with “unknown” target lesion response and assessments with unknown overall response will be excluded from the waterfall plots. Patients without any valid assessments will be completely excluded from the graphs.

The total number of patients displayed in the graph will be shown and this number will be used as the denominator for calculating the percentages of patients with tumor shrinkage and tumor growth. Footnote will explain the reason for excluding some patients (due to absence of any valid assessment).

All possible assessment scenarios are described in [Table 2-4](#).

Table 2-3 Inclusion/exclusion of assessments used in waterfall graph

	Criteria for inclusion/exclusion			Possible sources of contradictions	
case	Target response	Overall lesion response	Include in waterfall?	Non-target response	New lesion?

1	CR/PR/SD	PD	Yes but as ' only	PD	any
2	CR/PR/SD	PD	Yes but as ' only	any	Yes
3	UNK	UNK or PD	No	any	any
4	CR/PR/SD	UNK	No	UNK	No
5	CR/PR/SD	CR/PR/SD	Yes as a bar	SD/IR	No
6	PD	PD	Yes as a bar	any	any

Percentage change from baseline in the sum of diameters of all target lesions over the time will be displayed for individual patients.

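### The waterfall plot in SAP 2.5.4 has no cut at the start of further antineoplastic therapy, so shrinkage under a next drug can be shown and counted as PDR001 activity (minor, supportive display)

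*SAP*

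**What the plan says.** **Purpose and metric.** SAP 2.5.4 states "Waterfall graphs will be used to depict the anti-tumor activity". The bar is the per-patient best value: "These plots will display the best percentage change from baseline in the sum of diameters of all target lesions for each patient". Percentages are reported as well. The number of patients displayed is shown, and "this number will be used as the denominator for calculating the percentages of patients with tumor shrinkage and tumor growth".

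**Filters.** There are two, both based on lesion response at the scan in question:
- If the target lesions are CR, PR or SD but a new lesion or non-target worsening makes the overall response PD, then "As a conservative approach, such assessments will not be considered for display as bars in the graph".
- "Assessments with “unknown” target lesion response and assessments with unknown overall response will be excluded from the waterfall plots".

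The accompanying table has six cases and is presented as complete. Case 5 (target and overall response both CR, PR or SD) and case 6 (both PD) give bars. Cases 1 to 4 do not.

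**Window for BOR.** SAP 2.5.1 names the scans that count for BOR: "Tumor assessments performed before the start of any further antineoplastic therapy". Protocol Appendix 1, section 3.1 adds a stop at progression on continued treatment and a default of 30 days after the last dose. Both are also written for BOR.

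**Data available.** Protocol 7.1.8 keeps imaging patients who stop for reasons other than irRECIST PD, until "eventual irRECIST PD per BIRC even if new post treatment ANP is started". Under Protocol 4.1.1 this applies up to the primary analysis cut-off. SAP 2.1 uses all data in the database up to that cut-off.

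**The concern.** A best-value display depends on which scans are eligible. Here the eligibility rules say nothing about when the scan was taken or what the patient was receiving, while the protocol deliberately collects scans after a switch of therapy. A large reduction under the next drug is the kind of value that a best-change rule will select.

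At stake is attribution. In a single-arm trial no control arm would reveal that part of the shrinkage came from another treatment. The plot is labelled as anti-tumor activity, and a reported percentage with shrinkage is attached to it. A reader would credit both to PDR001.

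**Working it through.** The plan states no figure for this display, so there is none to reproduce. The check applies the written rules to hypothetical patients.

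**Inputs**
- Target response (Protocol Appendix 1, section 2.4.2): PR is a decrease of at least 30% from baseline. PD is an increase of at least 20% and at least 5 mm over the smallest sum.
- Overall response (Appendix 1, section 2.5): PD if target lesions or non-target lesions progress, or if a new lesion appears.
- Bar or no bar: the six cases in SAP 2.5.4.
- Change = (sum − baseline) / baseline. Baseline is taken as 100 mm in each patient.

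**Patient 1: no progression, stops PDR001, starts a new drug**
- Week 8: 105 mm, (105 − 100)/100 = +5%, SD, bar.
- Week 16: 108 mm, +8%, SD, bar.
- Week 24, new drug: 60 mm, (60 − 100)/100 = −40%, target PR and overall PR, case 5, bar.
- Best value as written: −40%. With a cut at new therapy: +5%.

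**Patient 2: target-lesion progression, then a new drug**
- Week 8: 105 mm, +5%, SD, bar.
- Week 16: 130 mm, +30%, PD by target lesions, case 6, bar.
- Weeks 24 and 32, new drug: 60 mm (−40%) and 55 mm (−45%), both PR, case 5, bars.
- Best value as written: −45%. With a cut at new therapy: +5%.

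This path assumes that a single week-16 progression did not already end imaging as irRECIST PD, and that RECIST 1.1 responses are still assigned at later scans. Patient 1 needs neither assumption.

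**Patient 3: progression by a new lesion that persists, then a new drug**
- Week 8: 105 mm, +5%, SD, bar.
- Week 16: 110 mm with a new lesion, overall PD, case 2, no bar.
- Week 24, new drug: 60 mm, overall still PD, case 2, no bar.
- Best value: +5% under both rules. The existing filter protects this patient.

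**Size.** Protocol 1.2.1.2 reports 95 well-differentiated patients in the full analysis set. If all are displayed, one patient whose bar turns from growth to shrinkage moves the percentage by 1/95 = 1.1 points. The number of such patients is not in the documents. An assumed range of 1 to 10 gives 1/95 to 10/95, or 1.1 to 10.5 points. A patient who already showed shrinkage on PDR001 would only get a longer bar.

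**What does not move.** ORR is built from BOR, which has its own cut at new therapy. Duration of response and the success rule do not use the waterfall.

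**The case against.** The strongest reply is that this is silence, not an instruction. The waterfall sits in SAP section 2.5, where 2.5.1 sets the BOR window, and 2.5.4 itself lists new therapy before the first post-baseline scan as a reason for unknown BOR. A programmer could carry that window over. This stands as far as it goes: nothing tells anyone to count scans under the next drug. But the SAP has no single window to inherit. For PFS (2.7.1 and 2.7.3) it does the opposite and ignores new therapy, and the general rule in 2.1 points to the literal reading.

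It is also fair that the plot is supportive, and that single-agent development in NET has already ended (Protocol, Amendment 3 rationale; SAP 1). That limits the severity.

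A reader might infer more than the documents support:
- *Every scan is eligible.* It is not. Cases 1 to 4 never give a bar.
- *The missing stop at RECIST 1.1 progression is the same fault.* For BOR, Appendix 1 does say "If the patient progressed but continues study treatment, further assessments are not considered for the determination of best overall response". But patients may continue PDR001 past that progression (Protocol 6.1.5.1), so later shrinkage can be shrinkage on PDR001. Whether to draw it is a convention.
- *A PR-sized bar in a patient with BOR of SD contradicts ORR.* Such bars arise anyway, because ORR needs confirmation (SAP 2.5.3) and the waterfall takes a single best value.
- *The individual change-over-time plot shares the fault.* It selects no best value and yields no shrinkage percentage.
- *Two to four bars would belong to the next drug.* That needs an assumed 10 to 20 exposed patients and the 18.8% response rate in Protocol 1.1.1 (10 × 0.188 = 1.9; 20 × 0.188 = 3.8). Protocol Table 1-1 gives 1.8% for the same treatment, hence 0.2 to 0.4. The 18.8% comes from midgut disease, while 30 of the 95 patients are thoracic and 33 pancreatic. No count can be defended.

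**Conclusion.** The point holds in a limited form. Followed as written, SAP 2.5.4 lets a case 5 scan under a next antineoplastic drug become a patient's bar and enter the shrinkage percentage, which misattributes that shrinkage to PDR001. This rests on reading 2.5.4 literally together with the all-data rule, and on some patients having such scans before the cut-off. The protocol allows for those scans but does not count them. Exposure is narrowed because follow-up imaging applies to patients who stop for reasons other than irRECIST PD and ends at irRECIST PD per central review.

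Severity is minor: the effect is confined to a supportive display and its two percentages.

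**What to change.** In SAP 2.5.4, add one sentence restricting the waterfall bars, and the percentages with shrinkage and growth, to assessments before the start of any further antineoplastic therapy, defined as for BOR in 2.5.1. The 2.5.1 treatment of limited-field palliative radiotherapy should carry over. Patients with no valid assessment in that window then leave the graph and its denominator, and the footnote already planned for exclusions can cover them.

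Two further changes are optional presentation choices: marking the start of new therapy on the individual over-time plots, and stopping the RECIST 1.1 waterfall at first RECIST 1.1 PD.

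The cost is the sentence plus reuse of a date filter that the BOR derivation already needs. The reported shrinkage percentage may fall slightly.

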Ph II Carcinoids and pNET study (n=109) (Kulke 2008)	Sunitinib (2L, prior chemo allowed)	Carcinoid (n=41) pNET (n=66)	Carcinoid: 2.4% pNET: 16.7%	mTTP**: carcinoid:10.2 mo pNET: 7.7 mo	1-yr OS rate Carcinoid: 83.4%; pNET:81.1%
Ph III pNET study (n=171) (Raymond 2011)	Sunitinib vs. Placebo (1:1)	G1/2 advanced pNET	Sunitinib: 9.3% Placebo: 0%	mPFS: Sunitinib:11.4 mo Placebo: 5.5 mo HR: 0.42 (p=0.001)	HR: 0.41 p=0.02
Ph III RADIANT-3 pNET study (n=410) (Yao 2011)	Everolimus vs. Placebo (pretreated SSA, Chemo)	Advanced, low or intermediate grade pNET	Everolimus: 4.8% Placebo 2.0%	mPFS: Everolimus: 11 mo Placebo: 4.6 mo	NR
Phase III NETTER-1 Midgut NET (n= 299) (Strosberg 2016)	PRRT + OCT vs. OCT	Advanced, well-differentiated Midgut	PRRT: 1.8% OCT: 3%	mPFS: PRRT: Not reached OCT: 8.4 mo HR: 0.209	NR
*NR = Not reported ** mTTP = median Time To Progression					

The treatment strategies of poorly-differentiated neuroendocrine carcinoma are often extrapolated from the treatment paradigm of small cell lung cancer (SCLC) (Sorbye 2014). There are no prospective studies conducted in gastroenteropancreatic neuroendocrine carcinoma (GEP-NEC), most of the studies reported are retrospective with limited sample size. Based on its established role in SCLC, cisplatin and etoposide is the most widely used regimen in GEP-NET in the front line setting with response rates in the range of 42% to 67% and median survival of approximately 15 to 19 months (Moertel 1991; Mirty 1999). More recent data suggest that the clinical outcome in patients with GEP-NEC may be worse than previously reported. In a retrospective study, 252 patients with advanced GEP-NEC received cisplatin/etoposide or carboplatin/ etoposide (Sorbye 2013) reporting an ORR of 31%, median PFS of 4 months with a median survival of 11 months. No differences in outcome were observed when comparing cisplatin-based treatment versus carboplatin-based treatment. Upon progression on front line platinum based therapy, no standard therapy has been established for GEP-NEC. Retreatment with cisplatin is an option as well as different regimens are considered (including FOLFOX, XELOX, temozolamide plus capecitabine) as well as single agent therapy (including temozolamide, irinotecan, taxanes or amrubicin) (Garcia-Carbonero 2016). On small retrospective studies, the response rates ranges from 18% to 31%; with a median PFS of approximately 4 months and survival in the range of 6 to 9 months (Hadoux 2013; Hentic 2012; Olsen 2012).

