2.1 Data analysis general information

The interim and final analyses will be performed by Novartis. SAS version 9.4 or later software will be used to perform all data analyses and to generate tables, figures and listings.

There are 1 interim and a primary analysis planned for the primary efficacy endpoint.

The analysis cut-off date for the interim analysis will be established after 30 enrolled patients have completed 3 radiological assessments (approximately after 24 weeks of treatment) or have shown disease progression or have discontinued efficacy follow-up for any other reason. The analysis cut-off date for the primary analysis of study data will be 1 year after LPFT in the initially enrolled well-differentiated NET group. The primary analysis data will be summarized in the clinical study report (CSR).

For each of the analyses, all statistical analyses will be performed using all data collected in the database up to the data cutoff date. All data with an assessment date or event start date (e.g. vital sign assessment date or start date of an adverse event) prior to or on the cut-off date will be included in the analysis. Any data collected beyond the cut-off date will not be included in the analysis and will not be used for any derivations.

All events with start date before or on the cut-off date and end date after the cut-off date will be reported as ongoing. The same rule will be applied to events starting before or on the cut-off date and not having documented end date. This approach applies, in particular, to adverse event

and concomitant medication reports. For these events, the end date will not be imputed and therefore will not appear in the listings.

All analyses will be performed separately for the two groups of well-differentiated NET and poorly-differentiated GEP-NEC unless otherwise specified.

General analysis conventions

Pooling of centers: Unless specified otherwise, data from all study centers will be pooled for the analysis. Due to expected small number of patients enrolled at centers, no center effect will be assessed.

Qualitative data (e.g., gender, race, etc.) will be summarized by means of contingency tables; a missing category will be included as applicable. Percentages will be calculated using the number of patients in the relevant population or subgroup as the denominator.

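### The waterfall percentages for tumor shrinkage and growth are taken over displayed patients only, so both exceed the share of treated patients whenever someone has no valid scan

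*SAP*

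**What the plan says.** The waterfall part of SAP 2.5.4 sets these rules:

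- **Entry to the graph.** "Only patients with measurable disease at baseline will be included in the waterfall graphs".
- **Unknown assessments.** Those with unknown target lesion response are left out, and "assessments with unknown overall response will be excluded from the waterfall plots". In Table 2-3 (inclusion and exclusion of assessments), case 3 also leaves out an assessment with unknown target response and overall progression.
- **Patients left with nothing.** "Patients without any valid assessments will be completely excluded from the graphs".
- **Progression through a new or non-target lesion while the target lesions have not progressed.** No bar is drawn, but "A patient with only such assessments will be represented by a special symbol", so the patient remains displayed.
- **Denominator.** The number displayed is shown, and "this number will be used as the denominator for calculating the percentages of patients with tumor shrinkage and tumor growth".
- **Disclosure.** "Footnote will explain the reason for excluding some patients (due to absence of any valid assessment").

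For the primary endpoint, SAP 2.5.3 keeps patients without a valid assessment in the FAS and counts them as non-responders. DCR is also calculated on the FAS (SAP 2.7.1 and 2.7.2). No shrinkage percentage on the FAS is planned.

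**The concern.** The first scheduled post-baseline scan is at week 8. A patient who dies, or becomes too ill to be imaged, before any valid scan leaves the denominator and cannot be in the numerator. The exclusion can therefore depend on outcome. The printed percentage describes patients who reached an evaluable scan, not patients who were treated.

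The shrinkage percentage will stand in the same report as ORR and DCR, which keep these patients in the denominator. A reader who sets the figures side by side would be comparing different bases, and the waterfall figure has the more favourable one.

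Case 3 adds an inconsistency. A patient whose only evidence is overall progression with unknown target response is dropped, while a patient whose progression came through a new or non-target lesion with evaluable, non-progressing target lesions is kept as a symbol. The SAP calls the symbol rule conservative, but does not extend it to the first kind of progression.

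**Working it through.** **The plan's own figures.** No waterfall percentage is stated. The nearest figures are FAS-based, and they reproduce:

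- 9/90 = 10%, exact 95% CI 4.7 to 18.1, as in SAP 2.5.2.
- 7/95 = 7.4% and 1/21 = 4.8%, the response rates reported in Protocol 1.2.1.2. Reported response rates therefore use the FAS.

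**Inputs**

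- N: 95 well-differentiated NET and 21 GEP-NEC patients in the FAS (Protocol 1.2.1.2). Measurable disease is inclusion criterion 7, so the measurable-disease restriction should remove few.
- First scheduled scan: week 8, day 56 (SAP 2.7.3). A month is 30.4375 days (SAP 2.1.1), so day 56 is 56/30.4375 = 1.84 months.
- GEP-NEC after first-line therapy: "survival in the range of 6 to 9 months" (Protocol 1.1.1), read here as a median.
- Carcinoid and PNET on another PD-1 inhibitor: median OS 21 months (Protocol 1.1.1).
- m, the number with no valid assessment: not given for either group, so assumed.

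**Step 1: the factor.** If x patients show shrinkage, the plan prints x/(N-m) and the share of all N is x/N. The ratio is N/(N-m), which is above 1 as soon as m is 1. The growth percentage has the same denominator and the same factor, so the ratio of shrinkage to growth does not change.

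**Step 2: size for assumed x and m**

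| Group | x | m | x/N | x/(N-m) |
|---|---|---|---|---|
| GEP-NEC, N = 21 | 4 | 4 | 19.0% | 23.5% |
| GEP-NEC, N = 21 | 8 | 1 | 38.1% | 40.0% |
| GEP-NEC, N = 21 | 8 | 3 | 38.1% | 44.4% |
| GEP-NEC, N = 21 | 8 | 6 | 38.1% | 53.3% |
| NET, N = 95 | 38 | 5 | 40.0% | 42.2% |
| NET, N = 95 | 38 | 10 | 40.0% | 44.7% |
| NET, N = 95 | 38 | 19 | 40.0% | 50.0% |

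**Step 3: one way to get a plausible m.** Assume exponential survival and that everyone who dies before day 56 is unscanned. Then p = 1 - 0.5^(1.84/median), and the relative inflation is 1/(1-p) - 1.

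| Median survival | p | Expected m | Inflation |
|---|---|---|---|
| 6 months (GEP-NEC) | 0.191 | 21 × 0.191 = 4.0 | 24% |
| 9 months (GEP-NEC) | 0.132 | 21 × 0.132 = 2.8 | 15% |
| 21 months (NET) | 0.059 | 95 × 0.059 = 5.6 | 6% |

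At an equal excluded fraction the two groups have the same factor. The difference between them in step 3 comes only from the assumed early death rates, not from the smaller group size.

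**The case against.** The case for leaving the plan alone has several sound parts.

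- **The exclusion is disclosed.** The displayed number and a footnote are planned, and SAP 2.5.4 tabulates unknown best response by reason. A reader can roughly rebuild the FAS percentage. This stands, but it does not change the printed figure. It is also incomplete: a case 3 patient who progresses within 12 weeks has a best response of progression (Protocol Appendix 1, section 3.1), so does not appear in the unknown-response table.
- **No general rule is broken.** SAP 2.1 says "Percentages will be calculated using the number of patients in the relevant population or subgroup as the denominator". Displayed patients can be read as a subgroup, so a reader who infers a contradiction with SAP 2.1 goes too far. The contrast that matters is with SAP 2.5.3.
- **Many early deteriorations are scanned.** Protocol 7.2.3 requires prompt imaging on suspected progression, Table 7-1 asks for a scan at end of treatment if none is recent, and before the cut-off scanning continues after treatment stops. Progression with evaluable target lesions stays in the denominator as a bar or symbol. This stands and lowers m.
- **Not every exclusion reflects a poor outcome.** A change of imaging method can make an assessment unknown, and consent can be withdrawn. A reader might infer that those excluded are mainly early deaths. The documents give no breakdown to support that.
- **The effect is modest beside sampling error.** For 4/21 the exact 95% CI is 5.4% to 41.9%, and the shift to 4/17 is 4.5 points. This stands for precision. The shift nevertheless always goes one way.

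Two other items do not settle the matter. The Amendment 2 summary mentions deaths before the first tumor assessment, but it explains a criterion for a Part 2 that was later removed, concerns well-differentiated cohorts only and gives no count. The absence of fatal SAEs at the interim analysis does not rule out early deaths, because documented fatal progression is not to be reported as an SAE (Protocol 8.1.1).

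**Conclusion.** The point holds for the two waterfall percentages only. Each is N/(N-m) times the share of treated patients with measurable disease, N being their number, and therefore too high as a statement about that population whenever m is at least 1.

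A reader might go further and infer that the trial's antitumor activity is overstated. The documents do not support that. The primary ORR and the success rule use the FAS with these patients as non-responders, and growth is inflated by the same factor as shrinkage.

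A reader might also infer that GEP-NEC is affected most. That is plausible from the survival figures in the protocol, but no count by group is given. The 15% to 24% and 6% rest on exponential survival, on literature medians (for GEP-NEC, from small retrospective studies) and on no scan for anyone who dies before week 8. Prompt imaging would lower them; living patients who are unscanned or have only unknown assessments would raise them.

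This is an inexpensive improvement to a supportive display.

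**What to change.** In SAP 2.5.4, report the percentages with shrinkage and with growth on all FAS patients with measurable disease at baseline, as judged by the review that supplies the plot. Add a separate category, by reason and group, for no valid post-baseline assessment. It should include patients whose only assessments fall under case 3 of Table 2-3.

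The percentage on displayed patients may stay beside it, labelled as a description of the plot. Bars and symbols do not change.

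The new base would still not match ORR exactly, because SAP 2.5.1 keeps patients with only non-measurable disease in the ORR denominator. Inclusion criterion 7 should keep that difference small.

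The cost is one sentence in the SAP, one more annotation on the figure and a slightly less favourable shrinkage percentage. No new data are needed.
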